9 CHANGE FROM ANALYSIS PLANNED IN PROTOCOL

This section describes all changes from planned analyses in the protocol, after the protocol approval, but before the lock of the database, which did not lead to a protocol amendment.

1. Due to early termination of the trial, an abbreviated CSR will be produced instead of a full CSR and only a subset of all the statistical analyses that were planned in the protocol will be performed. . Following analyses have been excluded:
 - a. Evaluation of Antiviral effect: A listing showing the viral load data for Plaque assay and Rt-qPCR over time will be produced. Any other statistical analyses planned in the protocol, e.g. time-to-below the limit of quantification (BQL), time-to-undetectability, time-weighted average change from baseline up to Day 3 and Day 14, number and percent of subjects with undetectable RSV (from Day 1 to Day 14), number and percent of subjects with BQL and change from baseline in viral load, will not be performed
 - b. Evaluation of clinical activity:
 - i. No statistical analysis will be done on RDAI score, RACS and Global Severity Score (GSS)
 - ii. No statistical analyses will be included in the CSR on Clinical response, Adequate feeding , adequate oxygen supply
 - c. Correlation of immunogenicity: a listing of immunogenicity data (ADA and NAb) (as mentioned above in Section 8) will be produced. Statistical analysis for potential correlation between pre-Ab, TE ADA or NAb on safety, PK and efficacy, will not be performed. No descriptive summary statistics will be generated. There will also be no tabulation of prevalence of pre-Ab and incidence of ADA.
 - d. Evaluation of PD: The PD characteristics will not be reported in the abbreviated CSR (as serum levels of KL-6 will not be measured) and therefore no outputs will be produced
 - e. Parent(s)/Caregiver(s) assessment: No analysis will be done

10 CONVENTIONS

10.1 Visit Windows

For post-baseline assessments, the CRF visit label will be used for the summaries. No windowing will be done.

For the full Schedule of Events refer to CSP, Version 3.0 (Page 24)

10.2 Computation of Derived Data

The following calculations and derivations will be used:

- Change from baseline of parameter: (visit value of parameter – baseline value of parameter)
 - If either the baseline or post-baseline value is missing, the change from baseline is set to missing.
- Duration of AE (days) = (end date - start date +1)

- If either the end or start date is incomplete or missing, the duration of AE is set to missing.
- If AE ongoing at the end of the trial then AE duration = trial termination date – AE start date + 1. In the listing the duration will be presented as ‘>x days’ rather than ‘x days’.
- Hospitalization or ICU duration (days) = discharge date/time – admision date/time
 - If either the end or start time is missing, the duration is calculated using the date part only then; duration = discharge date – admission date +1.
 - If the subject is still hospitalized or in ICU at the end of the trial then the duration = trial termination date – admission date +1
- Time since onset RSV signs and symptoms (days) = date of ICF – start date of symptom + 1.
- AE onset day = AE start date - first study drug administration date + 1 (when AE start date \geq first study drug administration date
 - If AE start date < first study drug administration date then; AE onset day = AE start date - first study drug administration date
- Duration of oxygen supplementation (hours) is defined as total time of reported oxygen supply according to oxygen supplementation form.
 - If the time is missing or the date is incomplete then the duration is set to missing.

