- The planned study duration for each subject is approximately 28 days.
- The maximum study drug treatment duration for each subject is 3 days.
- The completion of the study is defined as the last visit of the last subject (LSLV) participating in the study.

Study Population

Japanese infants and young children aged 28 days to <2 years with a gestational age \geq 33 weeks, hospitalized for and diagnosed with RSV LRTI (but otherwise healthy).

Number of Subjects

A total of 60 subjects will be randomized and treated in the study.

Inclusion Criteria

A subject will be eligible for study participation if he/she meets all of the following criteria at screening and randomization, unless specified otherwise.

1. Subject is a Japanese male or female infant or young child aged 28 days to <2 years with gestational age \geq 33 weeks at screening.
2. Subject is of Japanese descent, i.e., born in Japan to Japanese parents and has Japanese maternal and paternal grandparents.
3. Subject weighs between \geq 3.0 kg and <15.0 kg at screening.
4. Subject is otherwise healthy, but is hospitalized for and clinically diagnosed with RSV LRTI (bronchiolitis or broncho-pneumonia), i.e., showing typical clinical signs and symptoms such as tachypnea, wheezing, cough, crackles, use of accessory muscles and/or nasal flaring.
5. Subject has a positive RSV diagnostic test within 4 days of screening.*
6. Subject is expected to have to stay in the hospital for at least 24 hours (according to the Investigator's judgment at screening).
7. Symptoms likely related to RSV infection (i.e., the symptoms present need to be probably linked to the current RSV infection according to Investigator's judgment) have appeared within 4 days of screening and are not yet improving at screening and randomization.
8. Subject fulfils at least two of the following RSV disease severity criteria at screening and randomization:
 - Inadequate oral feeding that requires feeding support (i.e., nasogastric tube or intravenous [i.v.] line),
 - Inadequate oxygen saturation defined as:
 - Oxygen saturation (SpO_2) < 95% on room air or
 - Requiring oxygen supplementation to maintain adequate oxygen saturation with documented pre-supplementation value < 95%
 - Signs of respiratory distress defined as:
 - Respiratory rate \geq 50 breaths per minute in infants up to 12 months of age, and \geq 40 breaths per minute in children above 12 months and/ or
 - Moderate or marked respiratory muscle retractions

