4.1.2. RECORDING OF ADVERSE EVENTS

What will be collected	All AEs
Responsibility	Investigator's responsibility
Period of collection AEs	All AEs will be reported from the time a signed and dated ICF is obtained until completion of the subject's last visit.
How are AEs elicited	
Spontaneous, unsolicited reports:
 
 - by subject, parents/caregivers and/or healthcare staff, - by observation (by the Investigator and/or healthcare staff), - by routine open questioning of the subjects (or parents/caregivers) or by the Investigator (e.g., "Is there anything new that you wish to discuss?") - by reviewing the diary with the subject's parent(s)/caregiver(s).

Where are AEs recorded	Documented in the source documents and the eCRF
When are AEs recorded	Detailed guidance on when to complete AEs is given in the CRF completion guidelines document.

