1 INTRODUCTION

Study ALX0171-C203 is a randomized, double-blind, multicenter, multiple-dose study of ALX-0171 versus placebo along with standard of care in Japanese infants and young children aged 28 days to < 2 years hospitalized for RSV LRTI.

The purpose of statistical analysis plan (SAP) is to ensure that all the outputs which will be produced, and the statistical methodologies that will be used, are complete and appropriate to allow valid conclusions regarding the study objectives.

The analyses described are based on the final CSP Version 3.0 Section 5, dated, 13/Nov/2017. However, due to the halt of ALX0171 development in infants based on the results from the RESPIRE trial, this study was terminated early and an abbreviated CSR is planned instead of a Full CSR..

At the time of early termination, a total of 17 subjects were screened. 16 subjects were screened for cohort 1 out of whom 15 were enrolled and randomized; An IDMC meeting was held upon completion of this cohort. For cohort 2, 1 subject was screened but not randomized..

This SAP describes those analyses that will be performed for the abbreviated CSR.

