5 GENERAL CHARACTERISTICS

5.1 Subject Disposition

Subject disposition will be listed by subject and summarized (number and percentage of subjects) by treatment group and overall using all screened subjects. The tabulations will include the following information:

- Number of subjects randomized
- Number of subjects included in the safety population

Percentages will be based on the number of screened subjects.

In addition subject disposition will be summarized (number and percentage of subjects) by treatment group and overall using the safety population. The tabulations will include the following information:

- Number of subjects who completed the 3-day study treatment period
- Number of subjects who discontinued the study drug, with reasons for discontinuation
- Number of subjects who completed the trial
- Number of subjects who discontinued early from the trial, with reasons for termination

Percentages will be based on the number of subjects in the safety population.

Subject disposition by visit and by treatment group and overall will also be summarized (number and percentage of subjects) using the safety population.

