6.8 Hospitalization, ICU, Apnea and Ventilation

Duration of hospitalization will be summarized by treatment group. Hospitalization events will be described using Kaplan- Meier method; the number of events (the hospital discharge), number of censored values (subjects who are not discharged from the hospital at the time of early termination), median and quartiles of time to event with 95%CI will be summarized by treatment group.

The duration of hospitalization is defined as the difference between admission and discharge and will be computed in days using the following formula:

- For subjects who were discharged:
(Discharge date/time – admission date/time) / 86400
- For subjects who were still hospitalized or in ICU at the time of early termination, the censoring date will be the date of termination of the trial and the duration of hospitalization will be derived using the following formula
Trial termination date – admission date + 1

Missing time will be defined as follows for the calculation of duration:

- If the admission time is missing then it is estimated as 00:01

- If the discharge time is missing then it is estimated as 16:00

Hospitalization and ICU duration days, as well as apnea episodes and ventilation will be listed by subject.

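### SAP 10.2 counts ongoing AEs to an undefined trial termination date; if that is one date for the whole trial, the listed >x days can exceed what was observed

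*SAP*

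**What the plan says.** **The rule.** In SAP 10.2 a closed event has duration end date minus start date plus 1, and "If either the end or start date is incomplete or missing, the duration of AE is set to missing". An ongoing event is the exception: "If AE ongoing at the end of the trial then AE duration = trial termination date" minus the AE start date plus 1. The SAP then adds: "In the listing the duration will be presented as" >x days instead of x days. Section 10.2 does not say what the trial termination date is.

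**Where else the term appears.** SAP 6.8 covers children still in hospital or in the ICU when the trial was stopped early. For them "the censoring date will be the date of termination of the trial", and the formula beneath uses the same term as 10.2. By contrast, SAP 5.1 tabulates "Number of subjects who discontinued early from the trial, with reasons for termination", and Table 14.1.1.2, whose title refers to trial termination, counts each subject's own completion or discontinuation.

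**How long a child is observed.** Protocol 4.1.2 states "All AEs will be reported from the time a signed and dated ICF is obtained until completion of" the last visit of that subject. The protocol synopsis says "The planned study duration for each subject is approximately 28 days", and Protocol 3.6.1.7 puts the End of Study visit at Day 28 with a 2-day window either side. Protocol 4.1.3 separately asks investigators to follow reported events to their final outcome.

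**The order of events.** SAP section 1 reports that cohort 1 was filled with 15 randomized children. It continues: "An IDMC meeting was held upon completion of this cohort". One child was screened for cohort 2 but not randomized. No calendar dates are given.

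**The concern.** An entry of >x days tells the reader that the event was known to last at least x days. That is true only up to the last day on which someone recorded the event as open. The date on which a sponsor stops a trial is not an observation date for any particular child. If the programmer counts to it, the listing claims persistence over a period for which there may be no record. The size of the excess then depends on when the child was enrolled, not on the course of the event.

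The rule also sits badly with the rest of the SAP. Section 4.7 rules out imputing missing data, section 6.1 leaves missing or partial AE dates unfilled, and the line of 10.2 just before this rule sets the duration to missing when an end date is absent. Here an end point is supplied that may never have been observed.

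Safety is in the first-listed objective. With 15 randomized children, readers of the abbreviated report are likely to go through the AE listings entry by entry.

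**Working it through.** The plan states no figure to reproduce. The check is date arithmetic plus a comparison of how the SAP uses the term.

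**Inputs**
- AE start: Day 5 (example, assumed).
- Last visit: Day 28, window Day 26 to Day 30 (Protocol 3.6.1.7).
- G, the days from the child's last visit or contact to the termination date: not given, so assumed over a range from 0 to 337. The upper end is 365 − 28 = 337, taken from the planned overall length of about 12 months. That is a planning figure, not the actual length of the trial.

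**Formulas**
- Supported lower bound = last visit − AE start + 1.
- SAP value, trial-level reading = (last visit + G) − AE start + 1.
- Excess = SAP value − supported bound = G.

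**Numbers.** Supported bound: 28 − 5 + 1 = 24 days.

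| Assumed G (days) | Listing would print | Excess (days) |
|---|---|---|
| 0 | >24 | 0 |
| 7 | >31 | 7 |
| 30 | >54 | 30 |
| 90 | >114 | 90 |
| 180 | >204 | 180 |
| 337 | >361 | 337 |

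The visit window moves the supported bound to 22 days (Day 26) or 26 days (Day 30). The excess is still G. On the subject-level reading G = 0, and the rule is an ordinary censored duration.

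**Which reading is better supported.** SAP 6.8 puts the same term in its formula, describes it as the date the trial was terminated, and applies it to children in hospital when the trial stopped early. Sections 1 and 3.2 use early termination for the sponsor's stop. Section 5.1 and Table 14.1.1.2 point the other way, but they deal with disposition and supply no date for a duration formula. The trial-level reading is therefore the more natural one, though not the only one.

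**Is G above zero?** Between the filling of cohort 1 and the stop came an IDMC meeting and a cohort 2 screening. Under Protocol 3.1.1 the IDMC reviews a cohort once its last subject has finished or discontinued the 3-day treatment, not at Day 28, and recruitment pauses meanwhile. The earlier cohort 1 children had probably passed Day 28 before the stop. The last ones may not have, so G could be zero for them.

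**Where the value goes.** SAP 6.1 includes AE duration among the listing fields, and it appears in Listings 16.2.2.1 to 16.2.2.4. None of Tables 14.3.1.1 to 14.3.1.7 uses it.

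**The case against.** The strongest reply is that the term is undefined and may mean the child's own end of participation, in which case nothing is overstated. This stands as a possibility, and for that reason the point is conditional. It does not remove the need for a change, because the text leaves the programmer to choose between two readings.

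A second reply is that Protocol 4.1.3 requires events to be followed to final outcome, so an open event may have documented status after Day 28. That is fair, and a reader who infers that the children were simply unobserved after Day 28 goes too far. But follow-up does not turn the termination date into an observation date. If an outcome date was obtained, the rule is not triggered. If not, the last documented status is the valid bound.

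A third reply is that little depends on it. The > sign marks the value as censored, the listings also show start date and outcome, no table summarizes AE duration, and no formal testing is planned. All of this is correct and keeps the severity low.

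A reader might also infer that the listings will assert months of persistence, or that most or all treated children are affected. The documents do not support either statement. They give no termination, randomization or last-visit dates, and they do not say how many events, if any, remained open.

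**Conclusion.** The point holds in conditional form, at low severity. If the trial termination date in SAP 10.2 is one date for the whole trial, as 6.8 suggests, then >x days is not a valid lower bound for any child whose last visit or contact preceded it. The excess equals that gap exactly. A positive gap is likely for the earlier cohort 1 children and could be zero for others. Its size cannot be derived from the documents, and the figures in the table rest on assumed gaps.

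The effect is confined to individual entries in the AE listings. Incidence, severity, seriousness and relatedness are unaffected, as are all AE summary tables. On the subject-level reading there is no error, only a missing definition.

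**What to change.** In SAP 10.2, replace the trial termination date in the ongoing-AE rule with the subject's own last visit date, or a later documented AE status date where one is recorded. Keep the >x days display.

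Apply the same subject-level definition to ongoing hospital and ICU stays in 6.8 and 10.2, so that one term does not carry two meanings. If any hospital stay is still open, this would also alter its censoring time in the Kaplan-Meier estimates and in Table 14.3.5.1.

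The cost is a few lines of SAP text and a small programming change. Last visit dates are already part of the study record. A date of last AE follow-up is not among the AE variables in Protocol 4.1.3, so it should be used only where it exists, with the last visit as the default. On that basis no new data are needed.

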10.3 SAS procedures

Hospitalization events will be described using Kaplan- Meier method. The following SAS code will be used;

```
PROC LIFETEST data=XXX;
  TIME Study Day * Status(0);
  [Where Status = 0 means not discharge event for the subject]
  STRATA Treatment Group;
RUN;
```

12 PROGRAMMING CONSIDERATIONS

12.1 General

The following details the requirements and specifications for the programming and presentation of the TLFs, as set out in the TLF shells.

- A separate RTF document will be created for each TLF.
- All TLFs will be produced in a landscape format, as far as is feasible.
- The margin, page size specifications are stipulated below and will be used for the presentation of all TLFs:

Item:	Specification:
Page Layout	Landscape
Paper Size	A4 (21cm x 29.7cm)
Margins (Top, Bottom, Left and Right)	2.54 cm
Header	1.25 cm
Footer	1.25 cm

- The standard font size and font type are "8 point", "Courier New" for all TLFs.
- Every page of each output will have a header indicating the Sponsor name (i.e., Ablynx NV) and protocol number (i.e., ALX0171-C203) (to be presented as set out in the example below).
- Every page of each output will contain a footer indicating the program name and the date and time when the output was produced (to be presented as set out in the example below).
- Every page of each output will contain a page number written in the format "Page X of Y" (to be presented as set out in the example below).
- Numbering of TLFs will follow ICH E3 guidance
- The following treatment group labels will be used for all TLFs in the following order (any treatment group with no subjects will not be displayed):
 1. Placebo
 2. ALX-0171 1.5 mg

Dates and times will be listed using date format ' DDMMYYYY ' and 24h clock format 'hh:mm', respectively.

All tables will be decimal aligned.

For all outputs containing calculated changes from baseline, the reference point will be specified in a footnote.

For all outputs containing calculated percentages, the denominator for the percentages will be specified in a footnote.

12.2 Headers

The Headers will contain Information for the Sponsor, Study Identifier and [REDACTED] Study No.
An example is presented below:

Ablynx NV
ALX0171-C203/[REDACTED] 234611

Page X of Y
Confidential

12.3 Display Titles

The display titles will include the category (Table/Listing), the number, the title and the analysis population.

12.4 Column Headers

Column headers and column contents will be equally aligned. Column headers will be aligned left for Parameters and Statistics. Results columns will be centered.

12.5 Body of Data Display

12.6 General Conventions

The following general conventions will be applied:

1. Always put percentages between ().
2. If percentage is zero, don't print the percentage.
3. How to report missing data (eg, in demography table):
 - Include missing category without percentage and calculate % based on the number of subjects with available data

Gender, n (%)	N=12
Male	6 (60.0)
Female	4 (40.0)
Missing	2

4. AE TLFs: always report the MedDRA version in a footnote
5. If there's no data to be included in the output (e.g., no SAEs), add a line with 'No data to present'.

12.7 Table Conventions

The following conventions will be applied for summary tables:

- Units will be displayed (where available)
- For categorical variables, the number of observations and percentages between brackets will be displayed.
- All the categories of a categorical variable will be displayed, even if the number of observation is zero for a given category.
- If the number of observation is zero, then the percentage will not be displayed.
- The denominator on which the percentages are based will be indicated in footnote.
- In case of missing data, a missing category without percentage will be displayed.
- If there are no data to be described in the output (e.g, no SAEs), a line "no data to present" will be displayed.

- Sorting of AE summary tables: by decreasing frequency in SOC and PT (overall). If more than one term with the same frequency, then sort those terms alphabetically.
- Sorting of prior/concomitant medication summaries: by decreasing frequency (overall)

13 INDEX OF TABLES

13.1 General

Table 14.1.1.1: Subject disposition: Tabulation

Population: all screened population.

Table 14.1.1.2: Treatment and Trial termination: Tabulation

Population: safety population.

Table 14.1.1.3: Subject disposition by visit: Tabulation

Population: safety population.

Table 14.1.2.1: Demographic data: Tabulation and descriptive statistics

Population: safety population.

Table 14.1.2.2: Baseline disease characteristics: Tabulation and descriptive statistics

Population: safety population.

Table 14.1.2.3: Medical History

Population: safety population.

Table 14.1.2.4: Prior therapies by generic term

Population: safety population.

Table 14.1.2.5: Concomitant therapies by generic term

Population: safety population.

Table 14.1.2.6: Exposure to study medication: Tabulation

Population: safety population.

13.2 Safety: Adverse Events

Table 14.3.1.1: Treatment-emergent adverse events: Summary table

Population: safety population.

Table 14.3.1.2: Treatment-emergent adverse events: Tabulation of all adverse events

Population: safety population.

Table 14.3.1.3: Treatment-emergent adverse events: Tabulation of all adverse events by severity

Population: safety population.

Table 14.3.1.4: Treatment-emergent adverse events: Tabulation of serious adverse events

Population: safety population.

Table 14.3.1.5: Treatment-emergent adverse events: Tabulation of all adverse events by relationship to study drug

Population: safety population.

Table 14.3.1.6: Treatment-emergent adverse events: Tabulation of the events for which the study drug was discontinued

Population: safety population.

Table 14.3.1.7: Treatment-emergent adverse events: Tabulation of all non-serious adverse events

Population: safety population.

